**Table 3: Primary Analysis Overview**

Objective	Outcome		Hypothesis	Method of Analysis
	Name	Type		
To determine if a dedicated social worker within the fracture clinic setting reduces all-cause return visits to emergency room or urgent care centers over 6 months	Any all-cause visits to the emergency room or urgent care centers	Binary	Participants receiving social work support will have fewer return visits to emergency room and urgent care centers in the 6 months following enrollment.	Cox proportional hazards regression model

For secondary analyses, we will follow mixed effects linear regression modelling for the LIMB-Q and satisfaction with care to account for repeated measures, with treatment, time of assessment, and pre-specified variables prognostic of each outcome included as independent variables in fixed effects. Each model will also include a cluster indicator as the random intercept. These secondary outcomes will be summarized as adjusted mean differences between groups with corresponding 95% CIs.

We will use logistic regression modeling for self-reported opioid use at 3 and 6 months using. Self-reported opioid use will be included as the dependent variable and each model will include the treatment variable, cluster, and pre-specified variables prognostic of the outcome as independent variables. We will present results as adjusted odds ratios with corresponding 95% CIs.

We will conduct a cost-effectiveness analysis from the payer's (hospital) perspective incorporating both participant utilities and direct healthcare costs and intervention costs. We will obtain health utilities from the EQ-5D. Costs will include the cost of employing a social worker, as well as healthcare use costs, such as fracture clinic visits, emergency room visits, urgent care facilities, and hospitalizations. We will compare these costs between the social worker intervention versus usual care groups using a cost-effectiveness analysis framework. The SAP will provide additional details on economic analysis plans.

We will also descriptively report the interactions made between the social worker and participants regarding the medium of contact, themes discussed, and the number and types of referrals made.

**Table 4: Secondary Analyses Overview**

Objective	Outcome		Hypothesis	Method of Analysis
	Name	Type		
To determine if a dedicated social worker within the fracture clinic setting reduces negative psychological impact over 6 months	LIMB-Q Psychological scale	Continuous	Participants receiving social work support will have higher LIMB-Q Psychological scores over 6 months compared to participants receiving usual care.	Mixed effects linear regression
To determine if a dedicated social worker within the fracture clinic setting reduces negative financial impact over 6 months	LIMB-Q Financial Impacts scale	Continuous	Participants receiving social work support will have higher LIMB-Q Financial Impacts scores over 6 months compared to participants receiving usual care.	Mixed effects linear regression
To determine if a dedicated social worker within the fracture clinic setting increases patient satisfaction with care over 6 months	Satisfaction with care	Continuous	Participants receiving social work support will have higher level of satisfaction with their care compared to participants receiving usual care.	Mixed effects linear regression
To determine if a dedicated social worker within the fracture clinic setting reduces self-reported opioid use at 3 and 6 months	Opioid use at 3 months and 6 months	Binary	Participants receiving social work support will have lower opioid use at 3 and 6 months compared to participants receiving usual care.	Logistic regression
To determine if a dedicated social worker within the fracture clinic setting reduces the number of missed fracture clinic visits over 6 months	Missed clinic visits	Continuous	Participants receiving social work support will have fewer missed visits over 6 months compared to participants receiving usual care.	Negative binomial model
To determine the cost-effectiveness of having a dedicated social worker within the fracture clinic setting over 6 months	Cost-effectiveness analysis from a payer's perspective	Continuous	Social work support will result in higher utilities and lower cost compared to the usual care group over 6 months	Economic analysis

## 6.2 Sensitivity Analyses

We will conduct a sensitivity analysis to include only those participants who had at least one visit with a social worker. This analysis will follow the same analyses methods as described for the

primary outcome, including appropriate regression models and adjustments for stratification variables.

We will conduct a sensitivity analysis that varies definition of return to emergency room and urgent care centre to include only visits that occurred at the same hospital/health system where the participant is receiving care for their fracture (e.g. participating cluster location). This analysis will follow the same methods listed for the primary outcome, including appropriate regression models and adjustments for stratification variables.

We will conduct a third sensitivity analysis that will also vary the definition of return to the emergency room and urgent care centre to include all visits. We will follow mixed effects linear regression modeling to account for repeated measures, with treatment, time of assessment, and pre-specified variables prognostic of each outcome included as independent variables in fixed effects. The model will also include a cluster indicator as the random intercept. The outcome will be summarized as an adjusted mean difference between groups with corresponding 95% CIs.

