#### **4.4 Participant Eligibility Criteria**

The screening population for this trial is patients 18 years of age or older with an injury to the appendicular skeleton which occurred in past 12 weeks and required surgical management who present to a participating fracture clinic.

The inclusion criteria are:

1. Aged 18 or older.
2. Had a fracture of the appendicular skeleton.
3. Fracture required surgical management.
4. Fracture occurred within the past 12 weeks.
5. Willing to comply with the protocol.

The exclusion criteria are:

1. Incarceration.
2. Expected injury survival of less than 6 months.
3. Terminal illness with expected survival of less than 6 months.
4. Currently enrolled in a trial that does not permit co-enrollment.
5. Unable to engage in protocol in the languages available in the local cluster.
6. Prior enrollment in the trial.
7. Declined to provide informed consent.
8. Not approached at (or prior to) the first post-surgery fracture clinic visit (missed participant).
9. Other reason to exclude the patient, as approved by the Methods Centre.

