#### **4.6 Intervention**

Research personnel at each cluster will inform individual participants of their treatment allocation **after** they have provided informed consent. Participants enrolled during the usual care phase at their clinic will attend appointments as usual on a schedule determined by their surgeon and will not have access to social worker support in the fracture clinic.

Participants enrolled during the treatment phase at their clinic will receive social work support (see Table 1) for 6 months from the time of enrollment. They will have an intake appointment with the social worker before or during their initial fracture clinic visit to assess their needs, identify goals that they can address with the support of the social worker, and collaboratively formulate a personalized care plan tailored to their specific circumstances. The social worker will then implement the plan, which may involve educating participants and their support network, coordinating delivery of care and benefits, making referrals to community services, advocating for the participant, and providing emotional support and brief counselling. The social worker will be accessible to participants for 6 months post-enrollment, following up via telephone, telemedicine or in-person to evaluate the effectiveness of the care plan and offer sustained ongoing support. During this time, the social worker will make detailed notes on communication and referrals provided.

Table 1: Social Worker Support

1. Intake and Assessment: The social worker will complete a standardized intake assessment questionnaire that will ask the participant about their social needs. This will include asking about safety, intimate partner violence, addictions, housing and utilities, finances, food insecurity, mental health, transportation, and injury recovery.
2. Formulation of goals: Based on the intake and assessment, the social worker will work with the participant to identify goals the social worker can help the participant achieve. An example of a goal is “plans for childcare during physiotherapy appointments”; “manage my stress and anxiety since the car accident”; “help to stop drinking”; “try to get off pain medications”; or “get a walker while on a fixed income”.

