### 6.1 Outcomes Analysis

The primary and secondary analyses will be conducted following intention-to-treat (ITT) principles, ensuring that participants are analyzed in their originally assigned treatment groups, regardless of adherence or protocol deviations. Reporting of the trial results will follow the 2010 CONSORT statement and the extension statements for a batched, stepped-wedge cluster randomized trial.

For the primary analysis of time to any all-cause return visits to emergency room or urgent care centers, we will perform a Cox proportional hazards regression model, with treatment included as the independent variable, and cluster pre-specified variables prognostic of the outcome, such as pre-injury work status, included as covariates. Results will be presented as a hazard ratio and corresponding 95% confidence interval (CI) (**Table 3**).

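### Even with usual care kept as comparator, restricting the first sensitivity analysis to participants who saw the social worker selects one group on post-enrolment behaviour, and the estimate can be biased in either direction

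*Protocol*

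**What the plan says.** Protocol Section 6.2 defines the population of the first sensitivity analysis by contact: it will "include only those participants who had at least one visit with a social worker". On method it says "This analysis will follow the same analyses methods as described for the" primary outcome, which in Section 6.1 is a Cox model with treatment, cluster and prognostic covariates. Section 6.2 names no comparator for this analysis and no step to deal with who attends.

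Three other places bear on it:

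- **Analysis principle (6.1).** The primary and secondary analyses are intention-to-treat, "ensuring that participants are analyzed in their originally assigned treatment groups", "regardless of adherence or protocol deviations".
- **Order of events (4.4 and 4.6).** A patient is excluded if "Not approached at (or prior to) the first post-surgery fracture clinic visit". Participants learn their allocation after consent. Those enrolled in the treatment phase then have intake: "They will have an intake appointment with the social worker before or during their initial fracture clinic visit". After that, "The social worker will be accessible to participants for 6 months post-enrollment".
- **Usual care (4.6).** These participants "will not have access to social worker support in the fracture clinic". Section 9.1 lets them use other local social work, and Section 4.8.2 records contact with social workers outside the clinic.

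**The concern.** Taken word for word, the filter removes nearly all usual-care participants, because they have no fracture-clinic social worker to visit. The natural repair is to keep usual care whole and apply the filter to the intervention phase only. That repair restores a comparator but does not make the groups comparable.

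A visit with the trial social worker is a behaviour after enrolment, and it can be observed in one phase only. Usual care contains people who would not have attended had they been offered the service, and nothing identifies or removes them. If non-attenders differ in their risk of an emergency or urgent care visit, the two groups differ even when the intervention does nothing. The planned covariates remove only the part of that difference they explain.

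At stake is the reading of the result. If the restricted estimate is further from 1 than the intention-to-treat estimate, it may look like a stronger effect in those who received the service, when it may be selection.

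**Working it through.** **Inputs.** From Section 5.0: risk 14.8% in usual care and 10% under treatment. The protocol states neither the share of treatment-phase participants who never see the social worker (q) nor the ratio of non-attenders' to attenders' risk (r). Both are assumed below and varied. The protocol gives no figure for this analysis, so there is none to reproduce.

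**Design effect as a hazard ratio.** With proportional hazards and equal follow-up, HR = ln(1 − p1) / ln(1 − p0) = ln(0.90) / ln(0.852) = 0.66.

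**Null calculation.** Suppose there is no effect, so both phases have an overall risk of 14.8%. In the intervention phase this is a mixture:

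0.148 = (1 − q) × pa + q × r × pa, so pa = 0.148 / (1 − q + q × r),

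where pa is the attenders' risk. Comparing attenders with all usual care gives HR = ln(1 − pa) / ln(0.852). For q = 0.20 and r = 2: pa = 0.148 / 1.20 = 0.1233, and HR = ln(0.8767) / ln(0.852) = 0.82.

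| Attendance | r | pa | HR with no true effect |
|---|---|---|---|
| 95% | 1.5 | 0.148 / 1.025 = 14.4% | 0.97 |
| 90% | 1.5 | 0.148 / 1.05 = 14.1% | 0.95 |
| 90% | 2 | 0.148 / 1.10 = 13.5% | 0.90 |
| 80% | 2 | 0.148 / 1.20 = 12.3% | 0.82 |
| 70% | 2 | 0.148 / 1.30 = 11.4% | 0.75 |
| 95% | 0.67 | 0.148 / 0.9835 = 15.0% | 1.02 |
| 80% | 0.67 | 0.148 / 0.934 = 15.8% | 1.08 |
| 70% | 0.67 | 0.148 / 0.901 = 16.4% | 1.12 |

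Keeping all enrolled participants gives 1.00 in every row.

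**Against the design effect, on the log scale.** At 95% and r = 1.5: ln(0.974) / ln(0.658) = 0.06. At 80% and r = 2: ln(0.822) / ln(0.658) = 0.47. At 70% and r = 2: ln(0.755) / ln(0.658) = 0.67. At 80% and r = 0.67 the bias points to harm, at 0.18 of the target size.

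**False-positive rate.** A null simulation used the two-batch design (47 per cluster-period, 400 runs per setting, linear probability model with clinic and batch-period effects). A significant benefit, nominally 2.5%, appeared in 1–5% of runs with everyone kept. With attenders only and r = 2, it appeared in 4.5% at 90% attendance, 13.5% at 80% and 19.5% at 70%. The 90% result lies within the range seen with everyone kept.

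**Time before first contact.** With contact at enrolment there is no added bias (HR 1.00). If first contact is spread evenly over days 0 to 42 and an earlier emergency visit prevents contact half the time, the null HR is 0.94.

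**The case against.** The strongest reply has four parts.

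- **The comparator is supplied by the reader.** Section 6.2 does not say that attenders are compared with all usual care, and Section 6.0 calls the text a brief overview with detail to follow in the SAP. That stands as far as the comparator goes. The filter itself is fixed in the protocol, however, and naming usual care as comparator does not remove the selection.
- **Attendance may be high.** Intake is scheduled around the first clinic visit, for people who have consented and are willing to comply. This stands: near-complete attendance makes the bias small.
- **The direction is unknown.** A reader might infer that the analysis will manufacture a benefit. The documents do not support that. Participants with few social needs may be the ones who skip the visit, and the bias then runs towards harm. Covariate adjustment may also remove part of either bias.
- **Timing.** A reader might infer from the six months of access that much untreated time is counted as treated. The intake schedule in Section 4.6 speaks against this. The problem arises only when first contact is late, and it biases towards benefit only if an early event makes contact less likely. If an emergency visit prompts the first contact, the bias runs the other way.

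**Conclusion.** The point holds in a limited form. Section 6.2 selects the intervention group on a post-enrolment behaviour with no counterpart in usual care and applies the primary model unchanged, so the estimate can be biased in either direction. Over the assumed range, the null hazard ratio runs from 0.75 to 1.12, against a design value of about 0.66. It is 0.97 at 95% attendance with a risk ratio of 1.5. These sizes depend on attendance and risk contrasts that the protocol does not give, on proportional hazards, and on no covariate adjustment.

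A reader might go further and doubt the trial's main result, or call the restricted analysis worthless. Neither follows. The primary and secondary analyses are intention-to-treat, no decision rule rests on this analysis, and with near-complete attendance it would differ little from intention-to-treat. The protocol also does not state what the analysis is for, so a claim that it fails a stated purpose would go beyond the text.

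**What to change.** Replace the restriction in Section 6.2 with a complier-average effect on the 6-month risk of any emergency or urgent care visit:

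- Keep every participant.
- Use phase at enrolment as the instrument for at least one visit with the fracture-clinic trial social worker, conditional on clinic and enrolment period. Do not count outside social work as exposure.
- Report the result beside the intention-to-treat estimate.

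Because usual care has no access to the trial social worker, the estimate is in the simplest case the intention-to-treat risk difference divided by the attendance proportion. A difference of 14.8 − 10 = 4.8 points at an assumed 80% attendance gives 4.8 / 0.8 = 6.0 points, and a difference of zero stays zero.

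If the restricted analysis is kept, label it descriptive, state usual care as comparator, and say how any time before first contact is handled.

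The cost is a wording change and a standard analysis using the contact log already kept under Section 4.8.2. The downsides are a wider interval, a risk-scale estimand in place of the Cox hazard ratio, and the assumption, to be stated, that phase affects these visits only through contact with the trial social worker.

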## 2.0 OBJECTIVES

The primary objective of this trial is to determine if the integration of a dedicated social worker within the fracture clinic setting, compared to usual care, reduces all-cause visits to the emergency room or urgent care over 6 months.

The secondary objectives of this trial are to determine if the integration of a dedicated social worker within the fracture clinic setting, compared to usual care:

1. Reduces negative psychological impact;
2. Reduces negative financial impact;
3. Increases patient satisfaction with care;
4. Reduces opioid use; and
5. Reduces missed fracture clinic visits.

We will assess the economic value of the intervention from the hospital (payer) perspective. We will also explore the lived experiences of orthopaedic trauma patients, social workers, and health care professionals in fracture clinics through structured interviews.

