#### *4.8.2 Participant Follow-Up*

We will follow participants for 6 months after enrollment, as this aligns with the usual clinical follow-up timeline for orthopaedic injuries. Table 1 below indicates the timeline for baseline and follow-up completion of CRFs. Follow-up may be completed in-person at the fracture clinic, by telephone, by mail, or via secure electronic methods. Research personnel may also review the participant's medical records for emergency room and urgent care visits.

The social worker at each clinic will document the social work interactions by maintaining a log that documents each point of contact they have with each participant. This log will include the

medium of contact, themes discussed, and number of referrals made. At each trial follow-up visit, we will ask participants if they saw a social worker outside of the fracture clinic and document any care referrals that they received.

Table 1: Follow-up Schedule				
	Enrollment and Baseline	6 Weeks (Day 42) (22 to 62 days post-enrollment)	3 Months (Day 90) (63 to 117 days post-enrollment)	6 Months (Day 180) (118 to 242 days post-enrollment)
Demographics and comorbidities	X			
Injury and treatment details	X			
Social worker interactions and referrals		Ongoing		
Emergency room and urgent care visits		X	X	X
LIMB-Q Psychological Impacts Scale	X	X	X	X
LIMB-Q Financial Impacts Scale	X	X	X	X
Satisfaction with care question	X	X	X	X
Opioid use	X	X	X	X
Fracture clinic visit attendance	X	X	X	X
EQ-5D questionnaire	X	X	X	X
Hospital use questions	X	X	X	X

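### The all-visits sensitivity analysis reports a linear mixed-model mean difference that is not the 6-month effect and takes no account of individual follow-up time

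*Protocol*

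**What the plan says.** Section 6.2 plans a third sensitivity analysis that will "vary the definition of return to the emergency room and urgent care centre to include all visits". It then fixes the model:

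- Type: "We will follow mixed effects linear regression modeling to account for repeated measures".
- Fixed effects: "with treatment, time of assessment, and pre-specified variables prognostic of each outcome included as independent variables in fixed effects".
- Random effects: "The model will also include a cluster indicator as the random intercept". No participant effect is named.
- Result: "The outcome will be summarized as an adjusted mean difference between groups with corresponding 95% CIs".

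No treatment-by-time term, offset or person-time is mentioned. The specification is essentially the one that section 6.1 gives for LIMB-Q and satisfaction with care.

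The objective in section 2.0 is to learn whether the intervention "reduces all-cause visits to the emergency room or urgent care over 6 months". Section 4.7.1 has staff ask about visits at 6 weeks, 3 months and 6 months, review medical records, and record the date of each visit. The follow-up schedule in section 4.8.2 sets these contacts at days 42, 90 and 180. The permitted ranges are 22 to 62, 63 to 117, and, for the last contact, "118 to 242 days post-enrollment".

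For the other count outcome, missed clinic visits, Table 4 names a "Negative binomial model".

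**The concern.** A LIMB-Q score describes a state at one time point, so averaging a treatment difference over three assessments makes sense. A visit count is different: it builds up over an interval, and its size depends on how long the interval is. Putting visit counts into the score model raises three problems.

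1. The single coefficient averages differences that belong to intervals of unequal length, or to nested cumulative periods. A reader will probably take it as visits avoided per participant over 6 months, which it is not.
2. The time-of-assessment term absorbs the average interval length. It does not absorb one participant's shorter or longer follow-up, or loss to follow-up.
3. An absolute difference on an unstated time scale cannot be set beside the primary hazard ratio as a robustness check, which is what a sensitivity analysis is for.

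Repeat visits do not enter the primary analysis, which models time to a visit. This is the planned effect estimate that uses all of them, so its scale should be clear.

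**Working it through.** The protocol gives no expected figure for this analysis, so there is nothing of its own to reproduce.

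**Inputs.** Section 5.0: 14.8% (usual care) and 10% (intervention) with a visit. Section 4.8.2: nominal days 42, 90 and 180, hence intervals of 42, 90 - 42 = 48 and 180 - 90 = 90 days. My assumption: visits follow a Poisson process with a constant rate, and the two proportions apply to 6 months, as the protocol uses them.

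**Step 1: 6-month means.** Mean = -ln(1 - p).

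- Usual care: -ln(0.852) = 0.1602.
- Intervention: -ln(0.90) = 0.1054.
- Difference: -0.0548. Rate ratio: 0.1054/0.1602 = 0.66.

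**Step 2: by interval.** Mean x days/180.

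| Interval | Days | Usual care | Intervention | Difference |
|---|---|---|---|---|
| 0 to 42 | 42 | 0.0374 | 0.0246 | -0.0128 |
| 42 to 90 | 48 | 0.0427 | 0.0281 | -0.0146 |
| 90 to 180 | 90 | 0.0801 | 0.0527 | -0.0274 |
| Total | 180 | 0.1602 | 0.1054 | -0.0548 |

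**Step 3: what one coefficient estimates with complete data.** Section 6.2 does not say how visits are counted, so both readings are shown.

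- Per interval: (0.0128 + 0.0146 + 0.0274)/3 = 0.0183, one third of 0.0548. This ratio holds whatever the rate.
- Cumulative: (0.0128 + 0.0274 + 0.0548)/3 = 0.0317, or (42 + 90 + 180)/(3 x 180) = 58%. This ratio depends on the constant rate. It would fall to 33% if the whole difference arose after day 90, and rise to 100% if it all arose before day 42.

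A simulation of the linear mixed model (8 clusters, 2000 participants, per-interval counts, period terms added) agrees with the first reading. It gave -0.0176 against a total of -0.0520 with nominal contact days, and -0.0208 against -0.0606 with variable ones. The ratio is about 0.34 both times.

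**Range.** Using the other intervention-group proportions in Table 2:

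- 8%: 6-month difference 0.1602 - 0.0834 = 0.0768; coefficient 0.0256 (per interval) or 0.0444 (cumulative).
- 12%: 6-month difference 0.1602 - 0.1278 = 0.0323 before rounding of the terms; coefficient 0.0108 or 0.0187.

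**Step 4: exposure, if visits are counted to the actual contact date.** Total follow-up may be 118 to 242 days, a ratio of 242/118 = 2.05. The usual-care mean then runs from 0.1602 x 118/180 = 0.105 to 0.1602 x 242/180 = 0.215. Suppose visit rates are equal but the arms differ in mean day of last contact:

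- 10 days: false difference 0.1602 x 10/180 = 0.0089 visits, 16% of 0.0548.
- 20 days: 0.0178 visits, 32%.

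With per-interval counts, the false difference and the effect are both divided by three, so these percentages carry over to the coefficient.

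**Step 5: loss to follow-up.** If the planned 10% loss removed only the last assessment, equally in both arms, the coefficient would be about (0.0128 + 0.0146 + 0.9 x 0.0274)/2.9 = 0.0180 instead of 0.0183. Equal loss at the planned rate therefore matters little. Unequal timing or loss matters more.

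**The case against.** The strongest reply is that this is the third of three sensitivity analyses, that section 6.0 calls the text a brief overview with detail to follow in the SAP, and that a mean difference in visits is a legitimate absolute measure. That stands as to weight. It does not remove the point, because section 6.2 goes beyond an overview here: it fixes the model, its terms and the summary measure.

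Some stronger readings are tempting but are not supported.

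- **That the one-third ratio is a bias.** With complete per-interval counts it is a change of scale. Multiplying by three recovers the 6-month difference, and the sign and test are unaffected. The fault is that the scale is unstated and does not match the objective.
- **That the longest interval is under-weighted.** It supplies 0.0274/0.0548 = 50% of the coefficient, matching its 50% of the exposure.
- **That exposure certainly varies with contact dates.** The ranges in section 4.8.2 govern follow-up contacts. Section 4.7 limits the outcome to six months, and visit dates are recorded, so visits could be assigned to fixed intervals. The last interval could run from 1 day (117 to 118) to 179 days (63 to 242) only if counts run between contacts, and those are extreme pairings.
- **That rare counts invalidate the estimate.** Under Step 2, 92% to 96% of usual-care records would be zero, but non-normality alone does not bias a mean difference with about 2000 participants.
- **That only this analysis addresses the objective.** Table 3 pairs the objective with a binary any-visit outcome.

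**Conclusion.** The point holds in a limited form. Under a constant rate and the protocol's proportions, the reported mean difference would be about -0.018 (per interval) or -0.032 (cumulative), against about -0.055 visits per participant over 6 months. The one-third ratio needs only complete per-interval counts; the 58% also needs the constant rate. Individual follow-up time is not modelled. Bias from this requires that visits be counted to the contact date, or that loss to follow-up be incomplete in a way that differs between arms; the documents do not show that either will happen. The result also cannot be compared with the primary hazard ratio, and the choice of model is out of line with the protocol's treatment of missed clinic visits. Severity is low: the primary analysis and the sample size do not depend on this analysis, and nobody should infer that the primary result is at risk.

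**What to change.** Replace the model in section 6.2, or settle it in the SAP:

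- Outcome: each participant's total number of visits up to day 180, taken from the recorded visit dates.
- Model: negative binomial, with log(days observed, capped at 180) as offset and the same cluster and covariate terms as the primary model.
- Result: a rate ratio with 95% CI. Under the constant-rate assumption its target is 0.66, on the same footing as a hazard ratio.
- Observation time: state the date to which each participant's visits are ascertained, whether last contact or record review, so that the offset is well defined.

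A recurrent-event model with robust variance is an acceptable alternative. With one record per participant, the negative binomial version also avoids relying on a cluster-only random intercept to handle repeated measures.

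The cost is a change of wording, since visit dates are already collected. The main downside is that the result becomes a relative measure. If an absolute figure is wanted, a 6-month difference in visits can be derived from the fitted model.
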